7.6. Reporting SAEs

7.6.1. Timeframes for Reporting SAEs

The Investigator must report SAEs according to the following time frames:

• Death or Life-Threatening Event:

- *Initial notification* must be provided to the sponsor or designee **within 24 hours** of the Investigational site learning of the death or life-threatening event (regardless of causality).
- *Complete SAE information* (i.e., all SAE pages) must be sent to the manufacturer or designee within 48 hours
- Follow-up information must be sent to the sponsor or designee within 48 hours of receipt of the information by the Investigational site.

• All other SAEs

- Complete SAE information (i.e., all SAE pages) must be sent to the sponsor or designee within 24 hours
- Follow-up information must be sent to the sponsor or designee within 48 hours of receipt of the information by the Investigational site.

7.6.2. SAE Information to Report

At a minimum, SAE reports must contain the subject ID, the serious adverse event term, onset date, relationship to study drug, and a brief narrative of the event.

7.6.3. Clinical Laboratory Abnormalities and Other Abnormal Assessments as AEs and SAEs

The Investigator should exercise his or her medical and scientific judgment in deciding whether an abnormal laboratory finding or other abnormal assessment is clinically significant.

Abnormal laboratory findings (e.g., clinical chemistry, hematology, and urinalysis) or other abnormal assessments (e.g., ECGs, vital signs) that are judged by the Investigator as clinically significant must be recorded as AEs or SAEs if they meet the definition of an adverse event. Clinically significant abnormal laboratory findings or other abnormal assessments that are detected after study drug administration or that are present before study drug administration but worsen after study drug administration should be assessed for AE criteria.

7.6.4. Documenting AEs and SAEs

All adverse events, including SAEs, which occur after the first dose of study drug must be documented in the subject's medical records and on the CRF.

A separate set of SAE pages should be used for each SAE. However, if at the time of initial reporting, multiple SAEs are present that are temporally and/or clinically related, they may be reported on the same SAE page.

The Investigator should attempt to establish a diagnosis of the event based on signs, symptoms, and/or other clinical information. In such cases, the diagnosis should be documented as the AE and/or SAE term.

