1.1. Rationale for the Current Study

The research hypothesis is that subcutaneously administered furosemide will be an effective alternative to IV furosemide for hemodynamically stable chronic heart failure patients presenting with volume overload in the ambulatory setting. The significance of this research is finding a potential intervention that could help decrease heart failure hospitalizations and improve the quality of life for patients with chronic heart failure. In addition, we can decrease the costs associated with heart failure.

There is very little experience with subcutaneous administration of furosemide EP/USP (current form of commercially available furosemide injection solution). There are a few studies that show the delivery of subcutaneous furosemide by electric infusion pump in terminally ill patients is effective for weight loss and symptom improvement (1,2). A group in Spain was successfully able to resolve 41 episodes of decompensated heart failure in 24 elderly patients using continuous subcutaneous furosemide administered by elastomeric infusion pumps (2). They found that the elastomeric infusion pumps provided safe outpatient treatment without the need for daily monitoring. In addition, it helped prevent hospital admissions and decreased costs due to the low price of the devices. It was also a good alternative for patients with venipuncture failure and the inability to transition from intravenous to oral diuretics.

Furosemide USP has a pH of 8.3 -9.0 and may cause irritation and discomfort upon administration. A novel buffered formulation with a physiologic pH (7.4) is currently under development in support of a NDA submission later in 2015. The product is to be marketed with a wearable patch pump for a slow 5-hour administration to optimize 8-hour diuresis.

scPharmaceuticals, Inc. (Lexington, MA), the developer of the novel furosemide formulation and its drug delivery device, provided the following information. The pivotal clinical study with the buffered furosemide solution (Furosemide Injection Solution (SCP-101)) started in Q2 of 2015 in support of the NDA. This study is conducted in the United States in stable HF patients under IND 118,919.

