3. INVESTIGATIONAL PLAN

3.1. Overall Study Design and Plan

This clinical trial is a prospective, randomized, parallel-group pilot study comparing the intravenous administration of Furosemide Injection, USP, to subcutaneous administration of a buffered furosemide formulation – Furosemide Injection Solution (SCP-101), in patients presenting to the Johns Hopkins Hospital Heart Failure Bridge Clinic with decompensated heart failure. Patients presenting to the HFBC will be assessed to determine whether they need IV diuretics. If they need it, they will be screened for eligibility. If they are eligible, written informed consent will be provided. Patients will then be randomized to receive Furosemide Injection, USP intravenously, or SCP-101 delivered subcutaneously. The IV patients will get the usual care of the Heart Failure Bridge Clinic, which includes having an IV placed and delivery of a one-time dose of IV furosemide with the dose determined by the providers (maximum dose 160mg IV). The subcutaneous patients will receive 80mg of Furosemide Injection Solution, 8 mg/mL, administered subcutaneously over 5 hours (30mg in first hour and 12.5mg/hour for 4 hours).

Administration will take place with the BBraun Perfusor® Space Infusion Pump System and a standard commercial infusion set. Both groups of patients will be observed for 6 hours to assess diuresis. The goal will be to enroll a total of 40 patients, 20 in the IV furosemide group, and another 20 in the subcutaneous furosemide group. Vital signs and urine output

will be monitored closely for 6 hours. Patients will be asked to fill out a survey about their symptom improvement (Kansas City Cardiomyopathy questionnaire) and overall satisfaction related to the treatment experience. They will also be monitored for side effects including ototoxicity and discomfort at the access site (burning, itching, and pain). Electrolytes and renal function will be checked once after the patients receive diuretic therapy. Study participants will be on fluid restriction during the study, with no more than 100 ml of fluid consumed during the 6 hours.

Study Drug:

- *Furosemide Injection, USP:* Furosemide Injection, Solution, single dose determined by Investigator (maximum dose 160mg) administered intravenously by IV bolus over approximately 2 minutes (reference treatment).

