3.1.2. Safety Endpoints

- 1) Patient reported Pain
- 2) Increases in serum creatinine of 0.5 mg/dL or greater
- 3) Local skin reactions including hematoma, induration, infection, thrombosis, necrosis etc.
- 4) Occurrence of treatment-emergent Adverse Events (AEs) or Serious Adverse Events (SAEs)

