6.1.9. Injection Site Inspection

Study staff will inspect the injection site for erythema and edema using the Draize Scale which includes a 5-point scale for erythema and a 5-point scale for edema. (Appendix 3)

In addition to the Draize scale scoring, the investigator will assess the injection site area for other local reactions, including hematomas, thrombosis, induration, infection, necrosis, etc. The Investigator will rate the reactions as mild, moderate or severe and make an assessment as to causality.

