7. ADVERSE EVENTS

The Investigator is responsible for the detection and documentation of events meeting the definition of an AE or SAE as provided in this protocol. Only treatment-emergent AEs and SAEs (occurring after the first dose of study drug through the appropriate follow-up period) will be recorded in this study. Treatment Emergent AEs, will be assessed continuously after administration of study drug through discharge.

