Appendix 1: Time and Events Schedule

| Time and Events Table | Screening Phase | Pre-Dose | Start of Dosing | Dosing | 6 hours post Start of Dosing |
|---|--------------------|----------|--------------------|--------|---------------------------------|
| Informed Consent | Х | | | | |
| Confirmation of Eligibility | Х | | | | |
| Co-morbidity | Х | | | | |
| Cardio-Pulmonary Examination | Х | | | | |
| Serum Creatinine | Х | | | | Х |
| Weight and Height | Х | | | | |
| Vital Signs | Х | Х | Х | Х | Х |
| 12-lead EKG | Х | | | | |
| Collection and Measurement of Urine Voids | | | Х | Х | Х |
| Urine Sodium | | Х | | | Х |
| Clinical Chemistry | Х | | | | Х |
| BNP/NT ProBNP | | Х | | | Х |
| Study Drug Administration | | | Х | | Х |
| Injection Site Pain Assessment | | | | | Х |
| Injection Site Inspection | | Х | | | Х |
| Randomization to Treatment Sequence | Х | | | | |
| Kansas City Cardiomyopathy questionnaire | | Х | | | Х |
| Treatment Satisfaction Survey | | | | | Х |
| Treatment Emergent Serious Adverse Events | | | X | X | Х |

Verbally indicate the number on the Numeric Rating Scale that best represents the intensity of pain at or around the injection site NOW, with 0 being no pain and 10 being the worst possible pain.

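### Adverse events count only from the first dose, so access-placement events that resolve, occur at an abandoned site or prevent dosing have no defined place in a comparison of two routes

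*Combined protocol and SAP*

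**What the plan says.** - **Recording window.** Section 7 states: "Only treatment-emergent AEs and SAEs (occurring after the first dose of study drug through the appropriate follow-up period) will be recorded in this study". Section 7.6.4 repeats the starting point for the medical record and case report form: events "which occur after the first dose of study drug must be documented".
- **Place of access in the sequence.** Table 1 and Appendix 1 put randomization in the Screening Phase. Section 3.1 describes the IV arm as the clinic's usual care, "which includes having an IV placed and delivery of a one-time dose of IV furosemide". Subcutaneous access is not described step by step, but it too must precede the infusion.
- **Objective.** Section 2 makes adverse effects by route part of the secondary objective.
- **Other safety records.** Section 3.1.2 lists, apart from adverse events, patient-reported pain and "Local skin reactions including hematoma, induration, infection, thrombosis, necrosis etc", with no first-dose limit. Under section 6.1.9 "the investigator will assess the injection site area for other local reactions, including hematomas, thrombosis, induration, infection, necrosis, etc", rating severity and causality. In Appendix 1 the row "Injection Site Inspection" is marked at Pre-Dose and at 6 hours after the start of dosing. Section 8.3 tabulates pain and local reactions.
- **Pain.** Section 6.1.8 has one rating, at the end of the 6 hours. The scale after Appendix 1 asks about pain at that moment only.
- **Definition.** Section 7.1 counts as an adverse event a condition first detected after dosing, even if it was already present before the study began.

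**The concern.** The trial compares two ways of delivering furosemide, so gaining access belongs to the treatment being compared. An event window that opens at the first dose leaves out the interval in which access is attempted. A cut-off common to both arms is not neutral here: venous cannulation and subcutaneous needle placement are different procedures and need not have the same rates of pain, failure or local injury.

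The route comparison on adverse effects may therefore lack some placement events, possibly in unequal numbers. Section 8.3 plans descriptive safety summaries, so the counts by arm are themselves the result. The early stopping rule in section 4.4 also turns on a between-arm difference in access-site discomfort and pain, without saying whether discomfort at placement counts. An event not written down on the day is hard to recover later.

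**Working it through.** The plan states no figure to reproduce: it gives no access-event rate, and section 8.1 bases the sample size on clinical consideration. The check is textual, with a little arithmetic for scale.

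**Step 1: order of events.** Randomization (Screening Phase), then access placement, then first dose. The window in sections 7 and 7.6.4 opens at the third step, so placement is after randomization but outside the window.

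**Step 2: where each kind of placement event could be recorded.**

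| Event before first dose | Adverse-event record (sections 7, 7.6.4) | Other safety records |
|---|---|---|
| Hematoma, induration or other local reaction still present at 6 hours, at the site used | Outside the window as written; possibly inside under section 7.1 if first detected after dosing | Yes: 6-hour inspection (6.1.9), tabulated (8.3) |
| Pain still present at 6 hours | As above | Yes: 6-hour rating (6.1.8) |
| Insertion pain that has resolved | Outside | No: one rating, for present pain |
| Local reaction seen before dosing that then resolves | Outside; section 7.1 does not help, since it was detected before dosing | Only if the Pre-Dose inspection follows placement, which is not stated |
| Reaction at an abandoned site | Outside, unless first detected after dosing (7.1) | Not defined: the inspected site is not said to include it |
| Failed or repeated attempts | Outside, and not clearly an adverse event in any window | No field is called for |
| Access failure that prevents dosing | Window never opens | The 6-hour time point is counted from the start of dosing, so it never arises |

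**Step 3: the Pre-Dose inspection.** Neither schedule says whether it comes before or after placement. If before, a lasting placement reaction appears as new at 6 hours. If after, it is on the form before dosing and could be read as a pre-existing finding. The plan also does not say that the injection site includes the IV cannula site.

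**Step 4: scale.** Section 3.1 gives 20 patients per arm. Counting patients with an event, each one missed shifts that arm's observed proportion by 1/20 = 5 percentage points.

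The rates below are assumptions for events that escape every record. Expected number per arm = 20p; chance of at least one = 1 − (1 − p)^20.

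| Assumed rate p | Expected per arm of 20 | Chance of at least one |
|---|---|---|
| 5% | 1 | 64% |
| 10% | 2 | 88% |
| 20% | 4 | 98.8% |
| 30% | 6 | 99.9% |

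If none were recorded among 20, the one-sided 95% upper limit would be 1 − 0.05^(1/20) = 13.9%. That limit means something only if the events could have been recorded.

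**The case against.** The strongest reply is that the adverse-event log is only one of four safety endpoints. Pain and local reactions are listed separately with no first-dose limit, the site is inspected twice, access-site discomfort is monitored in both groups (section 3.1), and section 7.1 admits conditions detected after dosing. This stands. A reader might infer that all placement harms are dropped from the comparison. The documents do not support that, because a hematoma still present at 6 hours at the site used is recordable and would be tabulated.

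Three further points also stand.

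- A reader might infer that the Pre-Dose inspection turns placement reactions into baseline. No baseline adjustment is defined and the order is not stated, so this is a possibility only.
- A reader might infer that the loss falls mainly on the IV arm and so biases the comparison in a known direction. The documents give no access-event rate for either arm. The phrase "a good alternative for patients with venipuncture failure" in section 1.1 reports another group's experience with elastomeric pumps; it is not a hypothesis of this trial.
- A failed attempt is not clearly an adverse event, since section 7.1 excludes procedures. Moving the window alone would not capture attempts; they need their own field.

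What the reply does not reach are the events in the lower rows of the Step 2 table. Section 7.1 helps only with conditions first detected after dosing, and its fit with the first-dose limit in sections 7 and 7.6.4 is itself unresolved. For abnormal assessments, section 7.6.3 takes up pre-dose findings only if they worsen.

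**Conclusion.** The point holds in limited form. The first-dose start excludes the access step from the adverse-event record, although that step is part of each randomized route. The separate local-reaction and pain endpoints recover lasting harms. They do not reliably recover events that resolve before 6 hours, occur at an abandoned site, are seen before dosing and fade, or prevent dosing.

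The loss need not be equal between arms, but its size and direction cannot be stated from the documents. The firm figure is 5 percentage points per missed patient in an arm of 20; the table of rates is illustration. The conclusion rests on reading the first-dose limit as written and on subcutaneous access preceding the infusion. In a 40-patient pilot with descriptive safety summaries this is a cheap improvement. The primary endpoints are not affected.

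**What to change.** 1. In sections 7 and 7.6.4, start the window for access-related events at the first access attempt after randomization, in both arms. Keep the first dose as the start for all other events.
2. Reconcile that wording with section 7.1, so that it is clear how a condition arising before dosing but detected afterwards is classified.
3. In section 6.1.9 and Appendix 1, state that the inspection covers the IV site as well as the subcutaneous site, including any site where access was attempted and abandoned. State that the Pre-Dose inspection is done before access placement, so that a placement reaction is not read as baseline.
4. Record the number of attempts and any failed access on the case report form. Tabulate them by arm beside the local site reactions, with all randomized patients as the denominator, in keeping with the intention-to-treat statement in section 8.2.

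The cost is one protocol sentence, a few clarifying phrases and a few form fields, with no added visit or procedure. A pain rating at placement would be an optional extra; without it, insertion pain can still be noted as an access-related event under the wider window.

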7.6.5. Regulatory/Ethics reporting requirement

The Investigator must comply with the applicable local regulatory requirements related to the reporting of SAEs to the IRB.

The sponsor of the IND must report SAEs and AEs to the FDA in accordance with 21CFR312.32.

8. STATISTICS

8.1. Determination of Sample Size

For this pilot study, the determination of sample size was primarily based on clinical consideration; with the aim to yield meaningful preliminary data.

8.2. Statistical Analysis Plan

A full statistical analysis plan will be developed. All data will be analyzed as intention-totreat. Continuous variables will be presented as mean \pm standard deviation and will be compared using the Students *t*-test (2-tailed), unpaired. Differences between treatment groups for the categorical variables will be analyzed using the chi-square test. For the purposes of this study, *P* values $\leq .05$ will be considered significant.

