3.1.1. Endpoints

Primary Endpoints:

- 1) Total volume of voids over a 6-hour period
- 2) Total natriuresis over a 6-hour period

Secondary endpoints:

- 1) Volume of voids between 0-2 hours, 2-4 hours and 4-6 hours post initiation of treatment.
- 2) Heart Failure Symptom Scoring/Symptom Improvement- (Kansas City Cardiomyopathy questionnaire)
- 3) Overall Satisfaction with Treatment- (Treatment Satisfaction Survey)

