6.1.2. Assessment of Safety

Evidence in Kidney Injury

Serum creatinine will be obtained just before administration and at the end of the 6 hour observation period.

Adverse Events

Incidence of Treatment-Emergent adverse events (AEs) or serious adverse events (SAEs) will be assessed. Treatment associated pain and any local skin reaction including hematoma, induration, infection, thrombosis, necrosis etc. will be assessed.

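### Both primary endpoints go to an unadjusted t-test although pre-dose creatinine is already collected; one pre-specified covariate could narrow the interval at little cost

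*Combined protocol and SAP*

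**What the plan says.** Section 3.1.1 names two primary endpoints: "Total volume of voids over a 6-hour period" and "Total natriuresis over a 6-hour period". Section 8.2 gives one rule for every continuous variable: summarise as mean and "standard deviation and will be compared using the Students *t*-test (2-tailed), unpaired". Significance is set at 0.05. No covariate is named anywhere. Section 8.2 also promises a full SAP, but no separate SAP text is included.

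On size, Section 3.1 states: "The goal will be to enroll a total of 40 patients, 20 in the IV furosemide group, and another 20 in the subcutaneous furosemide group". Section 8.1 explains that "the determination of sample size was primarily based on clinical consideration; with the aim to yield meaningful preliminary data". It gives no effect size, SD or power. Section 5.3.1 describes randomization in blocks of four and mentions no stratification factor. Section 5.5 makes the trial open label.

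On baseline data, Section 6.1.2 says: "Serum creatinine will be obtained just before administration and at the end of the 6 hour observation period". The schedule in Appendix 1 marks creatinine at Screening and at 6 hours, so on either reading a value exists before dosing. The same schedule marks "Weight and Height" at Screening and BNP/NT-proBNP at Pre-Dose.

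**The concern.** With no power basis for the sample size, the main product of this pilot is the estimated difference between arms and its confidence interval. The only variability figure in the documents, in Section 1, is an SD equal to half the mean (1460 ± 730 mL), so with 20 per arm that interval will be wide.

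An unadjusted comparison leaves in the error term any outcome variance that a baseline variable could explain. Neither primary endpoint has a pre-treatment value of its own, because urine collection starts with treatment. Creatinine is a candidate covariate that every patient already provides. Its level may vary a good deal: Section 4.2 excludes a rise of more than 25% from baseline but sets no limit on the level itself, and Section 4.1 admits NYHA classes II to IV. If creatinine is related to 6-hour output, the planned test gives up precision that one pre-specified term would recover without new data.

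**Working it through.** The plan states no power or detectable difference, so there is no figure of its own to reproduce.

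**Inputs from the documents**
- 20 per arm, N = 40 (Section 3.1); two-sided alpha 0.05 (Section 8.2).
- SD 730 mL (Section 1). This comes from usual-care IV visits averaging 220 minutes, so the mL figures are illustrative for a 6-hour endpoint.

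**Assumptions not in the documents**
- R², the share of within-arm outcome variance that the covariate explains: 0 to 0.30.
- A difference of 500 mL, used only to illustrate power.

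**Unadjusted t-test**
- SE = 730 × √(2/20) = 231 mL.
- Half-width = t(0.975; 38) × SE = 2.024 × 230.8 = 467 mL, which is 32% of 1460 mL.
- Power for 500 mL (noncentral t) is 56%.

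**ANCOVA with k covariates**
- SE = 730 × √(1 − R²) × √(2/20) × √[(N − 3)/(N − k − 3)], with 38 − k degrees of freedom. The last factor allows for chance covariate imbalance between arms.
- For k = 1 that factor is √(37/36) and t(0.975; 37) = 2.026.

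| R² (assumed) | Half-width, one covariate | Relative to 467 mL | Power for 500 mL |
|---|---|---|---|
| 0 | 474 mL | 1.5% wider | 55% |
| 0.05 | 462 mL | 1% narrower | 57% |
| 0.10 | 450 mL | 4% narrower | 59% |
| 0.20 | 424 mL | 9% narrower | 64% |
| 0.30 | 397 mL | 15% narrower | 70% |

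A simulation with one covariate (6,000 trials per setting) gave half-width ratios of 1.014, 0.963, 0.907 and 0.849 at R² = 0, 0.10, 0.20 and 0.30, in agreement with the table.

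**Break-even R²**
- One covariate: 1 − (2.024/2.026)² × 36/37 ≈ 0.03.
- Three covariates (35 degrees of freedom, t = 2.030): 1 − (2.024/2.030)² × 34/37 ≈ 0.086. On variance alone it is 1 − 34/37 = 0.081. At R² = 0 the half-width is 489 mL, about 5% wider than unadjusted.

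**Validity**
- In simulation with three covariates (8,000 trials per setting), type I error was 4.6% to 5.6% for both methods.

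**Natriuresis**
- The documents give no SD. The relative changes above do not depend on the SD, so they apply to natriuresis at the same R².

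**The case against.** The strongest reply is that nothing is wrong with the planned test. A reader might infer that the unadjusted t-test is biased or inflates false positives. It does neither: the comparison is randomized and the simulated type I error is about 5%. This part of the reply stands in full.

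Second, the benefit depends on an R² that the documents do not supply. This also stands. At R² = 0.10 power moves only from 56% to 59%.

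Third, the dosing rules could weaken the covariate. Section 5.4 leaves the IV dose to the physician and fixes the subcutaneous dose. If physicians take renal function into account, the relation between creatinine and output may be flatter in the IV arm. As an illustration, assume R² = 0.20 in the subcutaneous arm, zero in the IV arm and equal SDs. The common slope is then half the subcutaneous slope, and the mean residual variance is (0.85 + 1.05)/2 = 0.95 of the total. The half-width is about 462 mL against 467 mL. This limits the expected gain but does not reverse it.

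Fourth, the study is a pilot and a full SAP is promised. That leaves room for the change but does not make it. The only method stated is unadjusted, and in an open-label trial a covariate chosen after outcomes are visible would carry little weight.

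Two stronger readings are tempting. One is that adjusting for creatinine, weight and BNP/NT-proBNP together costs nothing. With 40 patients, three covariates must explain about 8% to 9% of the variance before they help, and the documents do not fix which of BNP or NT-proBNP is assayed. The other is that chance imbalance is a separate harm. At a correlation of 0.45, a one-SE imbalance moves the difference by 0.45 × 231 = 104 mL, but that variation is already contained in the 467 mL half-width and should not be counted again.

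**Conclusion.** The point holds as a matter of precision, not validity. For one covariate the exchange is favourable: about 1.5% wider if creatinine explains nothing, against 4% to 15% narrower if it explains 10% to 30% of the variance, with break-even near 3%. The range of R² is an assumption, and the relation may be weaker in the IV arm. The mL values rest on a proxy SD from shorter, IV-only visits; the percentages do not. The documents do not support a claim of certain or costless gain, nor routine adjustment for every baseline variable collected. The change is worth making but is not a condition for a sound primary comparison.

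**What to change.** In Section 8.2 and in the promised SAP, before any outcome data are seen, make the primary analysis of 6-hour void volume and 6-hour natriuresis an ANCOVA with treatment arm and one fixed covariate: pre-dose serum creatinine on the log scale, or eGFR derived from it. State which form is used, which value counts as pre-dose (Section 6.1.2 and the schedule time it differently), and how a missing value is handled. Keep the unadjusted t-test as a sensitivity analysis. Do not add weight or BNP/NT-proBNP by default.

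The cost is a short addition to the text and one degree of freedom. No new measurement or patient is needed.
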